At the interim analysis (20 patients/arm), the incidence of death or mechanical ventilation, grade ≥ 3 elevations in liver transaminases, or neutropenia will be estimated. We assume that the underline rate is 40%, 10%, or 24% for the three incidences in placebo group respectively, and if the rate in duvelisib group is $\geq 15\%$ higher than that in the placebo group in either of the three incidences, the trial may be stopped due to the safety concern. It also translates to stop the study if 3 or more excess events in duvelisib group are observed in either of the three incidences. Operating Characteristics, the probability of trial stopping due to ≥ 3 excess events based one simulation study, is listed in the below table.

AEs	Underline event rate in Placebo arm	Underline event rate in Duvelisib arm						
		5%	10%	20%	30%	40%	50%	60%
death or mechanical ventilation	40%	0%	0.02%	0.7%	4.8%	16.6%	37.4%	62.7%
grade ≥ 3 elevations in liver transaminases	10%	0.79%	5.7%	32.8%	65.8%	87.9%	97.2%	99.7%
neutropenia	24%	0.07%	0.6%	7.3%	26.1%	52.7%	77.3%	92.6%

In addition to the study stopping rules based an interim analysis, the Independent Data Monitoring Committee (IDMC) will review, on a monthly basis, the number of Grade 3 and/or Grade 4 adverse events in each arm, including neutropenia and elevated transaminases, and consider stopping or suspending accrual to the study if the frequencies of Grade 3 or Grade 4 adverse events are significantly higher among subjects in the duvelisib arm compared with subjects in the control arm.

Analysis of Safety Data

The primary safety endpoints include death or mechanical ventilation, grade ≥ 3 elvation in liver transminases, and neutropenia within 4 weeks. The cumulative incidence rate of each safety endpoint will be calculated with 95% confidence interval by randomized arms, and compared by Fisher's exact test.

Handing of Missing Data

For the safety endpoints and secondary endpoints, missing data will not be imputed, summaries and analyses will be based on the observed cases. For the primary efficacy analysis, every effort will be made from the informed consent form design to clinical follow up to reduce the missing data. Patients withdraw consent before the primary endpoint can be measured will be replaced.

Demographics and Baseline Characteristics

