Summary statistics and frequencies for the following characteristics will be described by randomized arms: ECOG, Race, Ethnicity, Age, Sex, Body mass index (BMI), Medical history of hypertension, diabetes, asthma, chronic obstructive pulmonary disease, History of and treatment for cancer, History of coronary artery disease (prior MI, CABG, coronary artery stent, or medical management), History of prior pulmonary infections (TB, pneumonia, influenza), Allergies

Subgroup analyses

None

15.2 Data/specimens:

Source Documents

Source data is all information, original records of clinical findings, observations, or other activities in a clinical trial necessary for the reconstruction and evaluation of the trial. Examples include medical records (hospital records, office charts), laboratory results, imaging scans and reports, EKGs, patient diaries, videos, photographs, pharmacy dispensing, and other records, investigator or patient completed questionnaires involved in the clinical trial.

Case Report Forms

The case report form (CRF) will be the primary data collection instrument for the study. All data requested on the CRF will be recorded and all entries will be recorded into an electronic data capture system by authorized personnel. The principal investigator is responsible for assuring that the data entered into the CRF are complete, accurate and that entries are updated in a timely fashion. Data will be entered in the clinical research data management system – REDCap - per Winship SOP 4.2 Data Completion Metrics. REDCap will be used to record all study related information and data for all registered subjects, including their assigned patient ID. All data submitted must be accompanied by supporting source documents, where applicable and as outlined in the protocol-specific monitoring plan. Data completion will be reviewed monthly. In situations where there are significant delays of data completion, the Associate Director of Clinical Research or the Director of Clinical Trials may temporarily suspend enrollment. All data must be entered in the timeframe required at each site, but no later than 30 days following registration and each visit completion. All queries are to be resolved within 4 weeks of issue. The coordinating center multi-site coordinator will provide REDCap training and request access to the appropriate staff at the participating site.

Procedures to Ensure Capturing Data for the Primary End-point

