7. Outcome (not recovered/not resolved, recovered/resolved, recovering/resolving, recovered/resolved with sequelae, fatal, unknown)

Protocol Title: Duvelisib Ameliorates Manifestations of Pneumonia in Established Novel Coronavirus Infection (DAMPEN-CI)

If the event worsens the event should be reported a second time in the CRF noting the start date when the event worsens in toxicity. For grade 3 and 4 adverse events only, if improvement to a lower grade is determined a new entry for this event should be reported in the CRF noting the start date when the event improved from having been Grade 3 or Grade 4. For phase I studies any AE that constitutes a DLT should be reported like a grade 3 and 4 adverse event. All adverse events should be treated appropriately. If a concomitant medication or non-drug therapy is given, this action should be recorded on the Adverse Event CRF.

Once an adverse event is detected, it should be followed until its resolution or until it is judged to be permanent, and assessment should be made at each visit (or more frequently, if necessary) of any changes in severity, the suspected relationship to the study treatment, the interventions required to treat it, and the outcome. Laboratory abnormalities that constitute an Adverse event in their own right (are considered clinically significant, induce clinical signs or symptoms, require concomitant therapy or require changes in study treatment), should be recorded on the Adverse Events CRF.

Laboratory abnormalities, that do not meet the definition of an adverse event, should not be reported as adverse events.

A Grade 3 or 4 event (severe) as per CTCAE does not automatically indicate a SAE unless it meets the definition of serious as defined below and/or as per investigator's discretion. A dose-hold or medication for the lab abnormality may be required by the protocol in which case the lab abnormality would still, by definition, be an adverse event and must be reported as such. Any serious adverse event, or follow up to a serious adverse event, including death due to any cause whether or not related to the study drug, must be **submitted on an SAE form** and assessed by PI in order to determine reporting criteria to regulatory authorities, IRB, DSMC, FDA.

All serious adverse events collected during this time frame will also be reported to Verastem.

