The Independent Data monitoring Committee (IDMC) for this study is a part of the Winship Data Safety Monitoring Committee (DSMC). The DSMC functions independently within Winship Cancer Institute to conduct internal monitoring functions to ensure that research being conducted by Winship Cancer Institute Investigators produces high-quality scientific data in a manner consistent with good clinical practice (GCP) and appropriate regulations that govern clinical research. Depending on the risk level of the protocol, the DSMC review may occur every 6 months or annually. For studies deemed High Risk, initial study monitoring will occur within 6 months from the date of the first subject accrued, with 2 of the first 5 subjects being reviewed. Subsequent monitoring will occur in routine intervals per the Winship Data and Safety Monitoring Plan (DSMP). The DSMC will provide oversight for the conduct of this study based upon access to unblinded study data and will continuously monitor cumulative SAE provided by the PI on a monthly basis. A planned analysis for futility will be submitted to the DSMC after accrual of 40 subjects. The DSMC will meet in closed session with access to unblinded data that will be provided by the study statistician.

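### The monthly Grade 3/4 toxicity review has no matching entry deadline or named report, so it can lack recent non-serious events

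*Combined protocol and SAP*

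**What the plan says.** **The trigger.** Section 15.1, Stopping Rule for Safety, says the IDMC "will review, on a monthly basis, the number of Grade 3 and/or Grade 4 adverse events in each arm, including neutropenia and elevated transaminases". It is to consider stopping or suspending accrual if these are significantly more frequent on duvelisib. Apart from the single look at 20 patients per arm, this is the plan's only between-arm toxicity trigger.

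**The committee's data.** Section 16.3 says, in one sentence, that the DSMC, of which the IDMC is part, oversees the study with unblinded access to its data and "will continuously monitor cumulative SAE provided by the PI on a monthly basis". It adds: "The DSMC will meet in closed session with access to unblinded data that will be provided by the study statistician". Section 15.1 assigns the IDMC's reports to an independent statistical team. Section 16.3 also says that, depending on protocol risk, "the DSMC review may occur every 6 months or annually".

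**Severity and seriousness.** Section 16.2, Documenting Adverse Events: "A Grade 3 or 4 event (severe) as per CTCAE does not automatically indicate a SAE" unless it meets the definition of serious.

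**Entry limits.** Section 15.2, Case Report Forms, requires entry in REDCap "no later than 30 days following registration and each visit completion". For subsites, section 16.2 gives 14 calendar days for adverse events and section 22 gives 14 days for all data, both in OnCore. Subsite SAEs go to the coordinating center within 24 hours.

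**Laboratory events.** Section 16.2, Study-Specific AE/SAE Reporting, limits graded laboratory events to bilirubin, ALT, alkaline phosphatase, AST, leukopenia, lymphopenia, anemia and thrombocytopenia. Neutropenia is not listed.

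**The concern.** The monthly review is meant to catch liver and marrow toxicity before and after the interim look. An asymptomatic Grade 3 transaminase or neutrophil result can be non-serious. It then falls outside the one monthly item that section 16.3 names, and it travels with ordinary case report data. At the lead site, where the study begins, that data may be entered up to 30 days after the visit. This is as long as the review interval and twice the 14-day treatment course, so an entry made on time can describe a patient whose treatment is already over.

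The plan sets no data cut-off for the monthly review. Nor does it say who compiles non-serious Grade 3/4 counts by arm each month: section 15.1 points to an independent team, section 16.3 to the study statistician. Neutropenia is in both the monthly trigger and the interim safety rule, yet is missing from the list of laboratory events to be graded.

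At stake is how current and complete the trigger's data are while randomisation continues.

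**Working it through.** **The plan's own figures.** None is given for the monthly review. The only operating figures for these toxicities belong to the single look at 20 per arm. They reproduce as P(Z ≥ (3 − 20(pD − pP)) / √(20[pP(1 − pP) + pD(1 − pD)])). For transaminases at 10% v 30% this is (3 − 4)/√6.0 = −0.41, giving 65.85% against the stated 65.8%. That table does not bear on monthly timing, so the delay has to be worked out separately.

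**Inputs.**
- Accrual: five a month (section 15.1, Study design). As an upper case, 80 patients over the synopsis's approximate 12 months is 80/12 = 6.7 a month.
- Allocation: 1:1 (section 1.2).
- Entry lag: 30 days (section 15.2), or 14 days for subsite adverse events (section 16.2).
- Review interval: monthly, taken as 30 days.

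**Formulas.** Worst-case delay = entry lag + full wait for the next review. Patients randomised meanwhile = monthly accrual × 12/365.25 × delay; half are on duvelisib. Daily accrual is 5 × 12/365.25 = 0.164, or 0.219 in the upper case.

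| Case | Lag + wait (days) | Randomised at 5/month (duvelisib) | Randomised at 6.7/month (duvelisib) |
|---|---|---|---|
| Lead-site limit | 30 + 30 = 60 | 9.9 (4.9) | 13.1 (6.6) |
| Subsite AE limit | 14 + 30 = 44 | 7.2 (3.6) | 9.6 (4.8) |
| With a 7-day limit | 7 + 30 = 37 | 6.1 (3.0) | 8.1 (4.1) |
| SAE timeline, about 1 day | 1 + 30 = 31 | 5.1 (2.5) | 6.8 (3.4) |

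**Splitting the 60 days.** At five a month the 30-day entry lag accounts for 30 × 0.164 = 4.9 patients, and the 30-day review interval for the other 4.9. Only the first half can be reduced by faster entry.

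**What a 7-day limit saves.** At the lead site, 60 − 37 = 23 days, and 23 × 0.164 = 3.8 patients (1.9 on duvelisib). At subsites, 44 − 37 = 7 days, or 1.1 patients.

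**The case against.** The strongest reply is that sections 15.1 and 16.3 do not conflict. Section 15.1 is an explicit, study-specific commitment to monthly Grade 3/4 review by arm, and section 16.3 adds SAE monitoring to it. A reader might infer from the SAE wording that the committee sees only SAEs from a blinded PI. The documents do not support that: the same sentence grants unblinded access, the statistician supplies unblinded data in closed session, and section 15.1 has an independent team write the reports. This stands. But access is not a scheduled report with a cut-off, and it cannot show events not yet entered.

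A reader might also infer that toxicity review could be six-monthly or annual. That wording describes the general DSMC cycle by risk level, and two separate statements commit this study to monthly monitoring.

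Other points limit the weight:
- The 60 days combines the latest permitted entry with a full review wait.
- The trigger needs a significantly higher frequency, so one late event is not the same as late detection of a signal.
- Investigators must review laboratory abnormalities and may stop study drug for an individual patient (sections 16.2 and 4.2.5). Committee timing does not delay this.
- Section 15.2 provides monthly checks of data completion, and sections 16.3 and 22 describe monthly calls on toxicity. The calls reach the study team, not the committee.
- Section 16.2 elsewhere asks for all adverse events to be recorded, which could capture neutropenia. That sits awkwardly with the restricted list in the same section, and the two need reconciling.

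**Conclusion.** The point holds as a gap in timeliness and completeness. With every stated limit met, a monthly review can lack about a month of non-serious Grade 3/4 events from the lead site, and the list of laboratory events to be graded does not match a toxicity that the trigger names.

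The upper bound at five patients a month is about 60 days, or 10 further patients randomised (5 on duvelisib). Under the 14-day subsite limit it is about 44 days, or 7 patients. About 5 patients in each case follow from the monthly interval itself and would remain. At 6.7 a month the two bounds are 13 and 10 patients.

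These figures assume steady accrual, reviews 30 days apart, entry on the last permitted day, and a clock that starts at the visit where the event is recorded. They measure how stale the data can be, not the expected delay in detecting a true difference. The lack of a named author for the monthly report would be only a missing detail on its own; the entry limit is what makes the change worthwhile.

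**What to change.** **Section 15.2.** Require Grade ≥3 adverse events, and the underlying transaminase and neutrophil results, to be entered at all sites within a short fixed limit and before each monthly data cut. Seven days is an example; the documents do not supply a figure. Reconcile sections 15.2, 16.2 (Participating subsites) and 22 on both the limit (30 v 14 days) and the system (REDCap v OnCore).

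**Section 16.3.** Match the monthly item to section 15.1: cumulative SAEs plus all Grade ≥3 adverse events by arm, prepared by the independent statistical team, with the committee's unblinded access kept. Reconcile that team with the study statistician named in section 16.3. State that the monthly cycle governs toxicity review in this study.

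**Section 16.2, Study-Specific AE/SAE Reporting.** Add neutropenia to the laboratory list so that it matches the trigger and the interim safety rule.

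**Cost and gain.** The cost is wording changes and faster entry of Grade ≥3 events by existing coordinators, using the existing committee, statisticians and databases. With a 7-day limit the lead-site worst case falls from about 10 patients to about 6, a saving of about 4 (2 on duvelisib). No dose, stopping threshold or treatment rule changes.

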Validated definition for severe disease (<https://covid19treatmentguidelines.nih.gov/overview/management-ofcovid-19/>) is based on the following:

Confirmed SARS-CoV-2 infection (by PCR test) with fever or suspected respiratory infection, plus one of the following:

- a. respiratory rate > 30 breaths/min;
- b. severe respiratory distress; or
- c. SpO₂ ≤ 93% on room air at sea level or PaO₂/FiO₂< 300.

APPENDIX B: POTENT INHIBITORS AND INDUCERS OF CYP3A4 (FDA reference 2014)

Effect on CYP3A	Drug Class	Medications
Moderate to Strong CYP3A Inhibitors	Antibiotics	chloramphenicol, ciprofloxacin, clarithromycin, erythromycin, telithromycin
	Antiemetic	aprepitant
	Antifungals	ketoconazole, fluconazole, itraconazole, posaconazole, voriconazole
	Antiviral protease inhibitors	amprenavir, atazanavir, boceprevir, cobicistat, darunavir, elvitegravir, fosamprenavir, indinavir, lopinavir, nefinavir, ritonavir, saquinavir, telaprevir, tenofovir, tipranavir
	Calcium-channel blockers	diltiazem, mibefradil, verapamil
	Foods/herbs	grapefruit, grapefruit juice, Seville oranges
	Serotonin antagonist	nefazodone
	Tyrosine kinase inhibitor	imatinib
	Vasopressin antagonist	conivaptan
Moderate to Strong CYP3A Inducers	Antibiotics	nafcillin, rifampin
	Anticonvulsants	carbamazepine, phenobarbital, phenytoin
	Antiviral reverse transcriptase inhibitors	efavirenz, etravirine
	Endothelin receptor antagonist	bosentan
	Foods/herbs	St. John's wort
	Wakefulness-promoting agent	modafinil

APPENDIX C: CYP450 Substrates (FDA reference 2019)

CYP enzyme	Sensitive substrates	Moderately sensitive substrates
CYP1A2	alosetron, caffeine, duloxetine, melatonin, ramelteon, tasimelteon, tizanidine	clozapine, pirenzepine, ramosetron, theophylline
CYP2B6	bupropion	efavirenz
CYP2C8	repaglinide	montelukast, pioglitazone, rosiglitazone
CYP2C9	celecoxib	glimepiride, phenytoin, tolbutamide, warfarin
CYP2C19	S-mephénytoïn, omeprazole	diazepam, lansoprazole, rabeprazole, voriconazole
CYP2D6	atomoxetine, desipramine, dextromethorphan, eliglustat, nebivolol, nortriptyline, perphenazine, tolterodine, R-venlafaxine	encainide, imipramine, metoprolol, propafenone, propranolol, tramadol, trimipramine, S-venlafaxine

APPENDIX D: CYP3A Substrates (FDA reference 2019)

CYP enzyme	Sensitive substrates	Moderately sensitive substrates
CYP3A	alfentanil, avanafil, buspirone, conivaptan, darifenacin, darunavir, ebastine, everolimus, ibrutinib, lomitapide, lovastatin, midazolam, naloxegol, nisoldipine, saquinavir, simvastatin, sirolimus, tacrolimus, tipranavir, triazolam, vardenafil	alprazolam, aprepitant, atorvastatin, colchicine, eliglustat, pimozide, rilpivirine, rivaroxaban, tadalafil

APPENDIX E: Immunomodulator and Immunosuppressant

Class	Medication
IL6 inhibitors	Tocilizumab, sarilumab, siltuximab
TNF inhibitors	Adalimumab, certolizumab pegol, etanercept, golimumab, infliximab
Anti-IL-1 agents	Anakinra, canakinumab, rilonacept

JAK inhibitors	Baricitinib, fedratinib, ruxolitinib, tofacitinib, upadacitinib
-----------------------	---

APPENDIX F: Drug Accountability Form

Study ID:				
[Drug] Pill Record				
Subject Initials: _____		Subject ID: _____		
Instructions:				
Planned Daily Dose:   mg				
Day	Date	Time	# of Tablets taken	Comments
1				
2				
3				
4				
5				
6				
7				
8				
9				
10				
11				
12				
13				
14				
15				

APPENDIX G: Procedure protocol for analysis of T cells

Procedure Protocol for Analysis of T-Cells for Protocol Duvelisib Antagonizes Manifestations of Pneumonia in Established Novel Coronavirus Infection (DAMPEN-CI)

Cryopreservation with CryoStor Media:

1. Suspend cells to be cryopreserved using mechanical or enzymatic dissociation.
2. Centrifuge cells to obtain cell pellet.
3. Remove supernatant.

Note: Remove as much culture medium as possible to reduce dilution of the CryoStor medium.

4. Isolation - Add **cold (2–8 °C) CryoStor medium** to a cell concentration range of $0.5\text{--}10 \times 10^6$ cells/ml for standard cell culture protocols. A higher cell concentration is possible with testing.

Note: CryoStor media contain DMSO, no additives are necessary.

5. Pre-freeze - Incubate cell suspension at 2–8 °C for ~10 minutes.

6. Nucleation – Lower sample temperature to –80 °C.

- a. Use a controlled rate freezer (–1 °C /minute) or similar procedure for most mammalian cell systems.

- b. The freezer should be pre-cooled to 2–8 °C.

- c. Ice nucleation within the sample (seeding) should be initiated at approximately –5 °C using a liquid nitrogen burst program setting on the controlled rate freezer or mechanical agitation (flick or tap) of the cryovial/sample container after 15–20 minutes at –80 °C.

Alternative Nucleation Procedures – cells can be frozen using stepwise freezing procedures.

Stepwise freezing procedures include:

- a. 2 hours at –20 °C followed by 2 hours at –80 °C or

- b. 3–4 hours at –80 °C in an isopropanol freezing container. The isopropanol container should be pre-cooled to 2–8 °C

Ice nucleation - mechanical agitation (flick or tap) of the cryovial/sample container after 15–20 minutes at –80 °C.

7. Storage – Store the samples at liquid nitrogen temperatures (below –130 °C).

Note: Sample storage at –80 °C is only recommended.

8. Thawing - Thaw samples quickly in a 37 °C water bath. Sample should be thawed with gentle swirling of the sample until all visible ice has melted. Thaw time for a 1 ml sample in a cryovial is ~3 minutes. Note: DO NOT allow sample to warm above chilled temperatures (0–10 °C). Cryovials should be cool to the touch when removed from the water bath. Passive thaw is **not** recommended.

9. Dilute cell/CryoStor mixture immediately with appropriate culture medium. This can be performed in a single step. The dilution medium should be between 20–37 °C. A dilution ratio of 1:10 (sample: medium) or greater is recommended.

10. Plate cells appropriately.

11. Culture the cells or use immediately.

Shipment:

Patient samples from secondary sites will be shipped in real-time overnight on Monday-Wednesday so that samples will be received no later than Friday. Each sample will be shipped on adequate amounts of dry ice. Emory University will cover the cost for shipment of the patient samples

APPENDIX H: Table to guide the IDMC during review of potential toxicity in the duvelisib arm at the time of the interim safety analysis

Table 1: Approximate probability of observing excess instances of mechanical ventilation or death in the duvelisib treatment arm at the time of the interim analysis.

		True Underlying Duvelisib Rate								
		20%	25%	30%	35%	40%	45%	50%	55%	60%
Approximate probability of observing $\geq X$ excess instances of mechanical ventilation or death in the duvelisib arm compared to placebo	X = 0	7.9%	15.2%	25.2%	37.2%	50.0%	62.6%	73.9%	83.2%	90.2%
	X = 1	3.9%	8.6%	15.9%	25.7%	37.3%	50.0%	62.5%	73.9%	83.4%
	X = 2	1.7%	4.4%	9.1%	16.3%	25.9%	37.4%	50.0%	62.6%	74.1%
	X = 3	0.7%	2.0%	4.8%	9.5%	16.6%	26.1%	37.5%	50.0%	62.7%
	X = 4	0.2%	0.8%	2.3%	5.1%	9.8%	16.8%	26.1%	37.4%	50.0%

Note: The true underlying placebo rate is assumed to be 40% in this table
